3.1.3 Rationale for the Trial and Selected Subject Population

Molecular subtypes defined by hormonal receptor (HR) and HER2 status have not been well studied in inflammatory breast cancer (IBC). We characterized clinical parameters and long-term outcomes, and compared pathological complete response (pCR) rates by HR/HER2 subtype in a large IBC patient population. We retrospectively reviewed the records of patients diagnosed with IBC and treated at MD Anderson Cancer Center from January 1989 to January 2011. Of those, 527 patients had received neoadjuvant chemotherapy and had available information on estrogen receptor (ER), progesterone receptor (PR), and HER2 status. The overall pCR rate in stage III IBC was 15.2%, with the HR-positive/HER2-negative subtype showing the lowest rate (7.5%) and the

HR-negative/HER2-positive subtype, the highest (30.6%). The HR-negative, HER2-negative subtype (triple-negative breast cancer, TNBC) had the worst survival rate. HR-positive disease, irrespective of HER2 status, had poor prognosis that did not differ from that of the HR-negative/HER2-positive subtype with regard to OS or PFS⁷. The two year PFS is only 60% at two years for patients with HR-positive/HER2-negative subtype. These findings identify an unmet medical need and justify exploring a novel treatment in this population at high risk for disease relapse.

The extensive invasion of lymphatic vessels by tumor emboli in IBC patients suggests that the host immune surveillance system is suboptimal or that the tumor cells have lowered their immunogenicity through immunoediting resulting in their ability to avoid detection by the host. In the immunocompetent host, tumor cells must overcome both innate and adaptive immunologic defenses of the host. A recent publication from our group also suggests that immune pathways are active in IBC⁴. Consistent with our findings, other groups have shown that several major inflammatory signaling pathways are constitutively active in IBC and breast cancer. Among them, the NF-κB, COX-2, and JAK/STAT signaling systems seem to play a major role in the tumorigenesis of IBC. Inflammatory molecules such as interleukin-6 (IL-6), tumor necrosis factor alpha (TNF-α), and interferon gamma (IFN-γ) have been shown to contribute to malignant transformation in preclinical studies of IBC, while transforming growth factor beta (TFF-β), interleukins 8 and 1β, as well as TNF-α appear to play a role in proliferation, survival, epithelial-mesenchymal transition, invasion, and metastasis.

In an ongoing study to evaluate immune function in IBC patients, we found that the median number of dendritic cell (DC) precursors was significantly lower in breast cancer patients than in healthy female donors (HFDs). Moreover, the median number of myeloid-derived dendritic cells (mDCs) in the peripheral blood of locally advanced breast cancer (LABC), IBC, and metastatic IBC (MIBC) patients was lower than the number of mDCs in the peripheral blood of HFDs. Because mDC and plasmacytoid dendritic cell (pDC) subsets determine the type of helper (Th1/Th2) or cytotoxic (Tc1/Tc2) effector responses, our data suggest that Th1 and Tc1 responses are compromised in patients with LABC, IBC, and MIBC. We observed a significantly lower median number of pDCs in IBC and MIBC patients than in HFDs, but the same was not true for the median number of pDCs in LABC and MBC patients compared with the number of pDCs in HFDs. These data suggest that Th2 and Tc2 responses may be lower in IBC and MIBC patients than in HFDs⁵.

In addition, a total of 87 IBC patients treated with neoadjuvant chemotherapy were eligible for gene expression analysis: 59 patients had RD [residual disease (no pCR)] and 28 (32%) had a pCR. We compared the pCR and RD groups with respect to histoclinical features, molecular subtypes, and several GES. We identified two immune pathways (IFNα- and INFγ-pathways) as hyperactivated in samples from patients with pCR ($P = 0.015$ and $P = 0.001$ respectively, Mann-Whitney test), as well as three pathways (EGFR, P53, TGBβ) as hypoactivated in patients with pCR ($P = 0.015$, $P = 0.015$, $P = 0.004$, respectively). Transcription factor (TF) analysis revealed three transcription factors (STAT5: $P = 3.6E-05$, GLI: $P = 8.7E-04$, SMAD: $P = 9.6E-04$, Mann-Whitney test) as hypoactivated in samples from patients with pCR after correction with false discovery rate (FDR) inferior to 20%. In the learning set, significant analysis of microarrays (SAM) (FDR inferior to 25%) identified 124 differentially expressed probe sets (107 unique genes), between responders and nonresponders, all of which were overexpressed in samples with

pCR. Several processes related to T-cell- dependent immune responses were strongly overrepresented in this gene list, including the ‘T-cell receptor signaling’ canonical pathway⁶.

These data provide the rationale for using anti-PD-1 maintenance therapy to maintain the progression-free status for IBC patients with HR-positive/HER2-negative subtype. Chemotherapies, surgery, radiation therapy can debulk the disease volume but cannot be used for maintenance. Therefore, using an anti PD-1 monoclonal antibody combined with standard adjuvant hormonal therapy is a very promising approach for these patients for whom currently nothing else has been proven to sustain the initial response to treatment and is a significant unmet need for patients with HR positive primary inflammatory breast cancer.

3.1.4 Rationale for Dose Selection/Regimen/Modification

An open-label Phase I trial (Protocol 001) is being conducted to evaluate the safety and clinical activity of single agent MK-3475. The dose escalation portion of this trial evaluated three dose levels, 1 mg/kg, 3 mg/kg, and 10 mg/kg, administered every 2 weeks (Q2W) in subjects with advanced solid tumors. All three dose levels were well tolerated and no dose-limiting toxicities were observed. This first in human study of MK-3475 showed evidence of target engagement and objective evidence of tumor size reduction at all dose levels (1 mg/kg, 3 mg/kg and 10 mg/kg Q2W). No MTD has been identified to date. 10.0 mg/kg Q2W, the highest dose tested in PN001, will be the dose and schedule utilized in Cohorts A, B, C and D of this protocol to test for initial tumor activity. Recent data from other clinical studies within the MK-3475 program has shown that a lower dose of MK-3475 and a less frequent schedule may be sufficient for target engagement and clinical activity.

PK data analysis of MK-3475 administered Q2W and Q3W showed slow systemic clearance, limited volume of distribution, and a long half-life (refer to IB). Pharmacodynamic data (IL-2 release assay) suggested that peripheral target engagement is durable (>21 days). This early PK and pharmacodynamic data provides scientific rationale for testing a Q2W and Q3W dosing schedule.

A population pharmacokinetic analysis has been performed using serum concentration time data from 476 patients. Within the resulting population PK model, clearance and volume parameters of MK-3475 were found to be dependent on body weight. The relationship between clearance and body weight, with an allometric exponent of 0.59, is within the range observed for other antibodies and would support both body weight normalized dosing or a fixed dose across all body weights. MK-3475 has been found to have a wide therapeutic range based on the melanoma indication. The differences in exposure for a 200 mg fixed dose regimen relative to a 2 mg/kg Q3W body weight based regimen are anticipated to remain well within the established exposure margins of 0.5 – 5.0 for MK-3475 in the melanoma indication. The exposure margins are based on the notion of similar efficacy and safety in melanoma at 10 mg/kg Q3W vs. the proposed dose regimen of 2 mg/kg Q3W (i.e. 5-fold higher dose and exposure). The population PK evaluation revealed that there was no significant impact of tumor burden on exposure. In addition, exposure was similar between the NSCLC and melanoma indications. Therefore, there are no anticipated changes in exposure between different indication settings.

The rationale for further exploration of 2 mg/kg and comparable doses of pembrolizumab in solid tumors is based on: 1) similar efficacy and safety of pembrolizumab when dosed at either 2 mg/kg or 10 mg/kg Q3W in melanoma patients, 2) the flat exposure-response relationships of pembrolizumab for both efficacy and safety in the dose ranges of 2 mg/kg Q3W to 10 mg/kg Q3W, 3) the lack of effect of tumor burden or indication on distribution behavior of pembrolizumab (as assessed by the population PK model) and 4) the assumption that the dynamics of pembrolizumab target engagement will not vary meaningfully with tumor type.

The choice of the 200 mg Q3W as an appropriate dose for the switch to fixed dosing is based on simulations performed using the population PK model of pembrolizumab showing that the fixed dose of 200 mg every 3 weeks will provide exposures that 1) are optimally consistent with those obtained with the 2 mg/kg dose every 3 weeks, 2) will maintain individual patient exposures in the exposure range established in melanoma as associated with maximal efficacy response and 3) will maintain individual patients exposure in the exposure range established in melanoma that are well tolerated and safe.

A fixed dose regimen will simplify the dosing regimen to be more convenient for physicians and to reduce potential for dosing errors. A fixed dosing scheme will also reduce complexity in the logistical chain at treatment facilities and reduce wastage.

Apart from the phase 1 study with Pembrolizumab and SBRT that is already published, there is published safety data from the phase 3 study PACIFIC in non-small-cell lung cancer with the PD-1 antibody Durvalumab¹⁶. The PACIFIC study included stage III NSCLC patients who had not progressed following definitive chemoradiation and showed both an increase in PFS by 11 months in the Durvalumab group as well as no significant difference in toxicity between groups. Of specific note, the incidence of grade 3/4 pneumonitis was 3.4% versus 2.6% in the placebo arm. This is encouraging given that the majority of patients in that study received definitive lung radiation to a dose of 54-66Gy. For patients with IBC, post-mastectomy radiation is a key part of trimodality treatment, and our typical target dose for the chest wall is in this range, hence lung dose would be considerably less, so we would not expect significantly higher rates of pneumonitis as a result of the concurrent radiation.

3.1.5 Study Endpoint

Up to 40% of patients with HR positive IBC who received pre-operative chemotherapy who did not achieve pCR will eventually have disease progression. The goal of this clinical trial is to observe clinical activity signals of pembrolizumab for disease stabilization or control as a maintenance therapy when given with combinatorial adjuvant HR blockade. The efficacy endpoint is to evaluate pembrolizumab¹².

4.0 METHODOLOGY

4.1 Entry Criteria

In order to be eligible for participation in this trial, the subject must meet the following criteria:

4.1.1 Inclusion Criteria

1. Is willing and able to provide written informed consent for the trial.
2. Is a female or male and ≥ 18 years of age
3. Has histological confirmation of breast carcinoma.
4. Has confirmed inflammatory breast cancer by using international consensus criteria:

Onset	Rapid onset of breast erythema, edema and/or peau d'orange, and/or warm breast, with/without an underlying breast mass
Duration	History of such findings no more than 6 months
Extent	Erythema occupying at least 1/3 of whole breast
Pathology	Pathologic confirmation of invasive carcinoma

5. Did not achieve pathological complete response (pCR) to any chemotherapy that was given with the intention to induce best response prior surgery. pCR is defined as the current American Joint Committee on Cancer (AJCC) breast cancer staging.
6. Is HER2 normal, defined as HER2 0 or 1+ by IHC and negative by FISH if performed; or HER2 is 2+ by IHC and negative by FISH; or HER2 negative by FISH if IHC is not performed.
7. Has positive ER or PR status. ER or PR $\geq 10\%$
8. Has a performance status of 0-1 on the ECOG Performance Scale.
9. Has adequate organ function as determined by the following laboratory values:
ANC $\geq 1,500 / \text{mcL}$, Platelets $\geq 100,000 / \text{mcL}$, Hgb $\geq 9 \text{ g/dL}$, creatinine levels $< 1.5 \times \text{ULN}$, Total bilirubin $\leq 1.5 \times \text{ULN}$, ALT and AST $\leq 2.5 \times \text{ULN}$
10. Subjects of reproductive potential must agree to avoid becoming pregnant or impregnating a partner, respectively, while receiving study drug and for 120 days after the last dose of study drug by complying with one of the following: (1) practice abstinence[†] from heterosexual activity; OR (2) use (or have their partner use) acceptable contraception during heterosexual activity.

Acceptable methods of contraception are: Single method (one of the following is acceptable): (1) intrauterine device (IUD); (2) vasectomy of a female subject's male partner; (3) contraceptive rod implanted into the skin. Combination method (requires use of two of the following): (1) diaphragm with spermicide (cannot be used in conjunction with cervical

cap/spermicide); (2) cervical cap with spermicide (nulliparous women only); (3) contraceptive sponge (nulliparous women only); (4) male condom or female condom (cannot be used together); (5) hormonal contraceptive: oral contraceptive pill (estrogen/progestin pill or progestin-only pill), contraceptive skin patch, vaginal contraceptive ring, or subcutaneous contraceptive injection.

Female subjects will be considered of non-reproductive potential if they are either:

(1) postmenopausal (defined as at least 12 months with no menses without an alternative medical cause; in women < 45 years of age a high follicle stimulating hormone (FSH) level in the postmenopausal range may be used to confirm a postmenopausal state in women not using hormonal contraception or hormonal replacement therapy. In the absence of 12 months of amenorrhea, a single FSH measurement is insufficient.); OR (2) have had a hysterectomy and/or bilateral oophorectomy, bilateral salpingectomy or bilateral tubal ligation/occlusion, at least 6 weeks prior to screening; OR (3) has a congenital or acquired condition that prevents childbearing.

Male subjects will be considered to be of non-reproductive potential if they have azoospermia (whether due to having had a vasectomy or due to an underlying medical condition).

11. Has negative serum or urine pregnancy test for subjects of childbearing potential within 10 days before first dose.
12. Have completed radiation (if candidate for post-mastectomy radiation) or plans to begin radiation and endocrine therapy within 28 days.
13. If the patient has already started hormonal blockade therapy after radiation as adjuvant therapy, the patient is eligible as long as the hormonal therapy was initiated no more than 6 months before the screening day and the patient can start the study drug within 4 weeks since the completion of screening.

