4.2.1 Dose Selection

4.2.1.1 pembrolizumab: Each cycle is defined as 3-week interval. pembrolizumab 200 mg will be administered on day 1 of each cycle as approximately 30 minute IV infusion (treatment cycle intervals may be increased due to toxicity as described in Section [4.2.2](#)). Pembrolizumab may be administered up to 3 days before or after the scheduled Day 1 of each cycle due to administrative reasons.

The Procedures Manual contains specific instructions for pembrolizumab dose calculation, reconstitution, preparation of the infusion fluid, and administration.

4.2.1.2 Hormonal Therapy: The hormone receptor blockade agent would be on physicians' discretion including tamoxifen, exemestane, anastrozole, letrozole, LHRH agonist and combination with any of above.

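### The contraception criterion accepts estrogen and progestin products for female patients with ER/PR-positive cancer who are on hormone receptor blockade

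*Combined protocol and SAP*

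**What the plan says.** Section 4.1.1, item 10, requires subjects of reproductive potential, female or male, to abstain or to "use (or have their partner use) acceptable contraception during heterosexual activity". The duty holds "while receiving study drug and for 120 days after the last dose of study drug".

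- **Single methods:** an IUD, "vasectomy of a female subject's male partner", or a "contraceptive rod implanted into the skin".
- **Combination methods:** under "Combination method (requires use of two of the following"), the list gives the diaphragm, cervical cap, sponge, condom and, as item (5), "hormonal contraceptive: oral contraceptive pill (estrogen/progestin pill or progestin-only pill"), the skin patch, the vaginal ring and the subcutaneous injection.

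Item 7 of the same section reads "Has positive ER or PR status", with a 10% threshold. Section 4.2.1.2 leaves the endocrine agent to the physician, "including tamoxifen, exemestane, anastrozole, letrozole, LHRH agonist and combination with any of above". Section 3.1.1 explains that growth and survival of hormone receptor-positive breast cancer rest largely on the supply of female hormones.

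**The concern.** The trial adds pembrolizumab to treatment that blocks hormone signaling in tumors selected for carrying hormone receptors. The same protocol tells sites that an estrogen/progestin or progestin-only product is an acceptable contraceptive, without saying that this is meant only for the partners of male patients. A premenopausal patient could meet the criterion by taking the hormones whose action the regimen is meant to block.

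What is at stake is patient safety and the consistency of the regimen, not the statistical design. If it happened, the study database would not show it: section 10.1, item 6, keeps concomitant medication in the medical record only.

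**Working it through.** The plan states no figure on this point, so the check is mainly a comparison of passages.

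**1. Does item (5) reach female patients?** Both sexes are eligible (item 2), and one list serves both. Where a limit is meant, the list states it: vasectomy is tied to the male partner of a female subject, and the cap and sponge are restricted by parity. Item (5) has no limit. The paragraph on menopausal status of female subjects also qualifies FSH confirmation by whether the woman uses hormonal contraception, so the text allows that she might. Item (5) therefore covers female patients as well as partners of male patients.

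**2. Does it conflict with the regimen?** Receptor positivity is an entry condition (item 7), receptor blockade is study treatment (4.2.1.2), and section 3.1.1 says the disease depends largely on female hormones. The conflict is inferred from that statement; no passage states a contraindication. Section 3.1.1 defines the subtype by both estrogen and progesterone receptors, so it does not exempt progestins.

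**3. Is it barred elsewhere?** None of the 16 exclusion criteria in 4.1.2 names an estrogen, a progestin or a hormonal contraceptive. Section 4.3.2 lists only live vaccines and glucocorticoids. The visible text has no explicit prohibition.

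**4. The single methods.** The text does not say whether the rod or the IUD releases hormone. They matter only where they do.

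**5. How long the rule applies.** Inputs: 34 three-week cycles (flow chart note e), 24 months maximum treatment (4.2), 120 days after the last dose (item 10).
- 34 cycles: the last dose falls 33 × 21 = 693 days after the first; 693 + 120 = 813 days, or 26.7 months.
- Full 24 months of dosing: 730 + 120 = 850 days, or 27.9 months.

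This measures the length of the obligation, not harm. The flow chart marks one pregnancy test, at screening, and none on treatment.

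**6. What remains if hormonal methods are removed for female patients.** Label the combination methods diaphragm D, cap C, sponge S, condom M and hormonal H.
- Nulliparous: C(5,2) = 10 pairs, less the barred D + C, gives 9. Four contain H, so 5 remain.
- Parous (D, M and H only): 3 pairs. Two contain H, so 1 remains (D + M).

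Abstinence, partner vasectomy and a non-hormonal IUD remain open to both groups.

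**The case against.** The criterion is a permission with one purpose, preventing pregnancy. It directs no patient to a hormonal method, non-hormonal options are already listed, and item (5) has a proper use for partners of male patients. The physicians who prescribe the endocrine therapy also control this exposure:

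- Section 4.3 leaves final decisions on supportive therapy with the investigator or the patient's primary physician.
- Section 4.3.1 ties concomitant treatment to community standards.
- Section 4.3.2 confines other drugs to those judged medically necessary.
- The flow chart has a medication review at screening, where a pill or patch should come to light.

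The harm is inferred. The documents do not separate estrogen from progestin or discuss how contraceptives interact with each endocrine agent, and the argument is strongest for estrogen-containing products. Removing hormonal methods also costs something, since pregnancy on pembrolizumab is itself a risk.

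Most of this stands as a statement about likelihood: use is improbable and may never occur. It does not correct the sentence that staff apply and patients agree to. Adding a second method does not remove the hormone exposure. A change limited to estrogen would leave progestins accepted in tumors that may qualify on progesterone receptor alone. The pregnancy trade-off is real and belongs in the fix.

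**Conclusion.** The concern holds. Item 10 accepts estrogen and progestin products for female patients whose disease and treatment, on the protocol's own account, argue against them, and no visible text overrides it. The number affected is unknown and may be zero. Its ceiling is the number of female subjects of reproductive potential among the 37, which the documents do not give. No effect on DFS is computed or claimed.

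The conclusion rests on reading item (5) as written and on taking section 3.1.1's description of the disease to apply to hormones taken as contraceptives. The Procedures Manual and the consent pages were not available and might say more. The criterion should be corrected because the change is cheap and the text is wrong for this population, not because harm has been shown.

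**What to change.** Amend inclusion criterion 10 only:

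- Limit combination item (5), and any rod or IUD that releases hormone, to female partners of male subjects.
- State that female subjects use abstinence, a non-hormonal IUD, partner vasectomy, or two of the listed barrier methods under the existing limits, through 120 days after the last dose.
- State that a female subject already on a hormonal method changes method and stays on study and in the DFS analysis.
- Discuss and confirm the method at screening, and at the next visit for anyone already enrolled on a hormonal method.

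Section 4.3.2 needs no addition. Sample size, monitoring rule and analysis are unaffected.

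There are two costs. Female subjects have fewer choices, and parous women are left with a single two-method pair. There may also be a small increase in pregnancy exposure on pembrolizumab. With no pregnancy test scheduled after screening, the discussion of method carries real weight.

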4.1.2 Exclusion Criteria

1. Is currently participating in a study of an investigational anti-cancer agent.
2. Has a diagnosis of immunodeficiency or any other form of immunosuppressive therapy.
3. Has not recovered from adverse events due to prior therapies, i.e. monoclonal antibody, chemotherapy, targeted small molecule therapy, radiation therapy, or surgery.
 - Note: Subjects with \leq Grade 2 neuropathy, alopecia and general disorders and administration site conditions (per CTCAE version 4.0) are an exception to this criterion and may qualify for the study.
4. Has a known history of prior malignancy with the exception of basal cell carcinoma of the skin, superficial bladder cancer, squamous cell carcinoma of the skin, or in situ cervical cancer, and has undergone potentially curative therapy and has no evidence of recurrence over the last 1 year since completion of curative therapy.

5. Has an active autoimmune disease requiring systemic treatment within the past 3 months or a documented history of clinically severe autoimmune disease, or immunosuppressive agents. Subjects with vitiligo or resolved childhood asthma/atopy would be an exception to this rule. Subjects that require intermittent use of bronchodilators, inhaled steroid or local steroid injections to the skin would not be excluded from the study. Subjects with hypothyroidism stable on hormone replacement or Sjögren's syndrome will not be excluded from the study.
6. Has a history of (non-infectious) pneumonitis that required steroids or current pneumonitis.
7. Has an active infection requiring systemic therapy.
8. Has known psychiatric or substance abuse disorders that would interfere with cooperation with the requirements of the trial.
9. Has received prior therapy with an anti-PD-1, anti-PD-L1, anti-PD-L2, anti-CD137, or anti-Cytotoxic T-lymphocyte-associated antigen-4 (CTLA-4) antibody (including ipilimumab or any other antibody or drug specifically targeting T-cell co-stimulation or checkpoint pathways).
10. Has a known history of Human Immunodeficiency Virus (HIV).
11. Has a known active Hepatitis B or Hepatitis C
12. Have received a live vaccine within 30 days prior to the first dose of trial treatment.
13. Gastrointestinal tract disease or defect or previous history of colitis.
14. Has proven or suspected distant metastasis that involves occurrence of breast cancer outside of loco-regional breast and lymph nodes area.
15. Subjects requiring daily corticosteroids either via po or infusion
16. Myocardial infarction within 6 months before starting therapy, symptomatic congestive heart failure (New York Heart Association > class II), unstable angina, or unstable cardiac arrhythmia requiring medication.

